4.1. Primary Endpoint

4.1.1. The primary outcome will be safety and tolerability will be determined by type, frequency and duration of adverse events (AE) and serious adverse events (SAE) in subjects receiving valganciclovir versus placebo.

4.2. **Secondary Endpoints:** We will evaluate for trends in other clinical endpoints, as well as viral and immune endpoints over time in the valganciclovir group compared to the placebo group.

4.2.1. We will determine the change in pulmonary function tests including forced vital capacity (FVC) and diffusing capacity for carbon monoxide (DLCO) in the valganciclovir treated group compared to placebo during active treatment and post-treatment follow-up. PFTs will be measured at baseline, 3 months (12 weeks), 6, 9 and 12 months after randomization to determine the FVC slope (change in FVC over time) and change in diffusion capacity (DLCO).

4.2.2. We will determine the effect of valganciclovir therapy on viral load in cell-free BAL fluid.

4.2.2.1. We will evaluate the change from baseline in daytime oxygen requirements. Oxygen requirements will be measured at study visits baseline, 3, 6, 9, 12 months. At each study visit, while at rest, the subject will be placed on the amount of supplemental O₂ required at the enrollment visit. After 5 minutes, the SpO₂ on this supplemental flow rate will then be recorded and evaluated in comparison to baseline. In addition, the patient will have his/her supplemental oxygen requirement determined to maintain oxygen saturation $\geq 88\%$ at rest. The change in liters per minute flow rate in oxygen compared to baseline will be recorded.

4.2.3. Exercise capacity will be determined on the basis of the 6 minute walk test (6MWT). The principal exercise capacity measurement will be the change in distance until SpO₂ reaches 80% compared to baseline. 6 MWT will be measured at study visits baseline, 3, 6, 9, 12 months. The 6MWT will be performed using a standardized protocol while the subject is breathing room air (i.e. without supplemental oxygen).

4.2.4. Additional secondary endpoints will analyze the immune response to herpesviruses by analyzing PD-1 expression by T lymphocytes and quantifying CMV- and EBV-antigen specific CD8⁺ T cell immune responses.

5. Background and Significance

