Randomization will be to pirfenidone plus placebo or pirfenidone plus valganciclovir. We prefer to have all subjects on pirfenidone as the standard of care for this study since the majority of patients elect to be treated with pirfenidone in our clinic. In addition, we anticipate valganciclovir will be better tolerated in combination with pirfenidone. We propose to enroll and randomize all eligible subjects with evidence of current or past EBV or CMV infection as determined by serologic testing for anti-EBV and CMV antibodies (total n=30) to treatment with pirfenidone plus valganciclovir (20 patients) or pirfenidone plus placebo (10 patients) for 12 weeks (**Fig. 1**). In order to maximize exposure to active treatment and assess for safety and tolerability, randomization will be 2:1 valganciclovir vs. placebo. The primary outcome will be safety and tolerability will be determined by type, frequency and duration of AE and SAEs. All study subjects will be offered bronchoscopy with BAL at study initiation and upon completion of treatment (12 weeks). Subjects will then be followed up at routine clinic visits at 6, 9 and 12 months for data collection.

[figure not shown]

Figure 1. Study flow chart.

6.2 **Rationale for Blinding and Placebo:**

6.1.1. A RCT is necessary given the clinical heterogeneity of IPF, and the inability to have two similar arms without randomization. A placebo arm will minimize bias since GI upset is a side effect of valganciclovir and standard treatment, pirfenidone. All subjects will be provided standard of care treatment to be applied equally across study groups as much as feasible and blinding will help avoid bias in the care provided.

6.1.2. Blinding is necessary to have optimal scientific validity, to make objective assessments of treatment effects, and to minimize dropout rates across study arms. In this study, there is particular concern that without blinding, subjects may opt to obtain off-label anti-viral therapy from non-study physicians if they become aware of the presence of herpesviruses in their lungs.

7. **Study population:** The study population will consist of male and female patients diagnosed with IPF, ages 21 and above, who are followed in the outpatient clinic setting.

7.1. **Inclusion criteria** will be:

- 7.1.1. age ≥ 21 and ≤ 80 years
- 7.1.2. ability to provided informed consent
- 7.1.3. diagnosis of probable or definite IPF according to ATS criteria(11)

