11.1.1. Rationale: This study is designed to assess for safety and tolerability of valganciclovir in IPF patients who are taking standard therapy for IPF (pirfenidone) as assessed by type, frequency and duration of AE and SAEs. Exploratory secondary analysis to evaluate for clinical efficacy will include changes in FVC slope of patients with IPF, oxygenation, and exercise capacity. In addition to identifying whether anti-viral therapy could positively impact any of these parameters, collecting these data will ensure that any detrimental effects of the drugs used to treat herpesviruses on clinically relevant endpoints will be identified. Information will be collected as outlined below. For analysis of all these variables, the standard treatment arm with pirfenidone and placebo will be compared to valganciclovir and pirfenidone.

11.1.2. Evaluation for safety of valganciclovir. Assessment of safety will be determined by ongoing review of clinical laboratory tests (blood sampling for clinical laboratory parameters-see schedule of events), physical examination including vital sign measurements, functional status assessments and adverse events. Women of childbearing potential will undergo a urine pregnancy test at each study visit.

11.1.3. Evaluation for treatment emergent adverse events. A treatment-emergent adverse event (TEAE) is defined as a sign or symptom that emerges during treatment or within the 12 weeks following the last dose of the study drug, having been absent pretreatment or that has worsened relative to the pre-treatment state. Any adverse event deemed related to study drug will also be considered a TEAE regardless of elapsed time since last study drug dose. Adverse events will be graded using National Cancer Institute [NCI] CTCAE Version 3.0 during the study evaluation. Study drug-related adverse events will be listed individually.

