13.2. Sample Size and Randomization

- 13.2.1. Power analysis: This pilot study is designed to determine tolerability and safety of valganciclovir as add-on therapy to pirfenidone. Pirfenidone is reported to be discontinued in 13% of subjects due to adverse events, almost all of which occur within the first 4 weeks of treatment (based on AE profiles from the ASCEND study). Therefore, we do not expect any

placebo treated subjects to withdraw from this study. Using a 2:1 randomization (valganciclovir:placebo) and enrolling 30 subjects will allow us to detect an increased withdrawal rate in the valganciclovir group in the range of 25% (75% power with a one-sided $\alpha=0.1$). Subjects who require dose reduction, or temporary discontinuation but are able to resume treatment will be considered non-withdrawals.

13.2.2. **Randomization:** The randomization scheme will be a ratio of 2:1 for drug versus placebo. Once a participant has signed the consent form and completed the enrollment visit (and baseline bronchoscopy in subjects who participate in the bronchoscopy substudy), the participant will be randomized. Study medication will be distributed by the VUMC investigational pharmacy according to the randomization scheme.

13.3. **Statistical analysis:** For the primary endpoint, the rate-of-discontinuation of study drug due to adverse events will be compared between valganciclovir and placebo subjects by Chi-square. **Secondary analysis:** Frequencies of specific adverse event profiles will be compared between groups by Chi-square. This study is not powered to detect clinically significant changes in pulmonary function or perform multivariate analyses. Exploratory analyses for physiologic and biochemical endpoints will be performed using standard nonparametric statistics or paired tests when appropriate. The rate of change in FVC (cc/year) will be compared between valganciclovir therapy group (treatment group) compared to the standard of care (placebo) group. For other physiologic measurements (6MWD, oxygenation), similar analyses will be performed. For exploratory biomarker studies, paired analyses (Baseline vs. 12 weeks) will be performed comparing subjects randomized to valganciclovir or placebo. All analyses will be performed using STATA 11.0 (StataCorp, College Station, TX) and the programming language R (50).

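### Section 11.1.1 says the physiologic data will ensure that any detrimental effect is identified, a property that 13.3 disclaims for pulmonary function and that 20 v 10 subjects cannot provide

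*Combined protocol and SAP*

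**What the plan says.** Section 11.1.1 (Rationale, Aim 1) introduces the physiologic measures as exploratory: "Exploratory secondary analysis to evaluate for clinical efficacy will include changes in FVC slope of patients with IPF, oxygenation, and exercise capacity". It then gives a second reason for collecting them: "collecting these data will ensure that any detrimental effects of the drugs used to treat herpesviruses on clinically relevant endpoints will be identified". The paragraph ends by saying that all these variables will be compared between the pirfenidone-plus-placebo arm and the pirfenidone-plus-valganciclovir arm, so the assurance rests on a between-arm comparison.

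Other sections are more modest:

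- Section 4.2: "We will evaluate for trends in other clinical endpoints, as well as viral and immune endpoints over time".
- Section 13.3, on power: "This study is not powered to detect clinically significant changes in pulmonary function or perform multivariate analyses".
- Section 13.3, on method: "Exploratory analyses for physiologic and biochemical endpoints will be performed using standard nonparametric statistics or paired tests when appropriate". It adds that the rate of change in FVC will be compared between arms, and "For other physiologic measurements (6MWD, oxygenation), similar analyses will be performed".

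Section 6.1 sets the size at 30 subjects, 20 on valganciclovir and 10 on placebo. The only power statement is in 13.2.1 and concerns withdrawal from the study. The documents give no SD, harm margin or power for any physiologic endpoint.

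**The concern.** Sections 11.1.1 and 13.3 cannot both stand for FVC. The first says that any detrimental effect will be identified; the second says the study lacks the power to detect even a clinically significant change in pulmonary function. The 13.3 disclaimer does not name oxygenation or walking distance, so for those the question is whether 20 v 10 subjects could support the assurance.

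This matters because safety and tolerability is the trial's stated aim, and 11.1.1 makes these endpoints part of the search for harm. Section 13.3 promises tests but no interval estimates. A non-significant comparison could then be reported beside the 11.1.1 sentence with nothing to show what size of harm the data had ruled out.

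**Working it through.** **Inputs from the documents.** 20 v 10 subjects (6.1); 2:1 allocation (13.2.2); one-sided alpha of 0.10, set for the withdrawal comparison only (13.2.1). No alpha is stated for the physiologic endpoints, so results are shown at both two-sided 5% and one-sided 10%.

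**Step 1: the plan's own power figure.** Section 13.2.1 gives 75% power for 25% v 0% withdrawal. With the pooled-variance normal approximation and no continuity correction:

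- pooled proportion = (20 × 0.25 + 10 × 0) / 30 = 0.1667
- SE under the null = √[0.1667 × 0.8333 × (1/20 + 1/10)] = 0.1443
- SE under the alternative = √(0.25 × 0.75 / 20) = 0.0968
- power = Φ[(0.25 − 1.2816 × 0.1443) / 0.0968] = Φ(0.672) = 74.9%

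The figure reproduces by this method. It says nothing about FVC, oxygenation or exercise.

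**Step 2: precision of an arm difference on a continuous endpoint.** In SD units the standard error is √(1/20 + 1/10) = 0.387. With 28 degrees of freedom the 97.5% point of t is 2.048, so the 95% half-width is 2.048 × 0.387 = 0.79 SD. Even if the observed difference were exactly zero, the interval would reach a harm of 0.79 SD.

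**Step 3: power.** Noncentral t, 28 df, noncentrality = d / 0.387, where d is the true harm in SD units:

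| True harm | Two-sided 5% | One-sided 10% |
|---|---|---|
| 0.3 SD | 11% | 30% |
| 0.5 SD | 24% | 50% |
| 0.8 SD | 51% | 77% |
| 1.0 SD | 70% | 90% |
| Harm detectable with 80% power | 1.12 SD | 0.83 SD |

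The t calculation stands in for the rank tests that 13.3 mentions, and assumes roughly normal data with equal SDs.

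**Step 4: illustration in mL, on assumed SDs.** The documents give no SD for annual FVC change. Assuming 200, 250 and 300 mL:

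| True excess decline | Test | SD 200 | SD 250 | SD 300 |
|---|---|---|---|---|
| 100 mL/year | Two-sided 5% | 24% | 17% | 13% |
| 100 mL/year | One-sided 10% | 50% | 40% | 33% |
| 200 mL/year | Two-sided 5% | 70% | 51% | 38% |
| 200 mL/year | One-sided 10% | 90% | 77% | 66% |

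All figures assume that all 30 subjects contribute; any dropout lowers them. During treatment, pulmonary function is scheduled only at baseline and week 12 (4.2.1, 10.8), so an on-treatment slope rests on two points.

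**The case against.** The strongest reply is that the plan already limits itself. Section 11.1.1 calls the analyses exploratory, 4.2 speaks of trends, and 13.3, the operative analysis section, disclaims power. The disputed sentence sits in a rationale paragraph and sets no test, margin or decision rule. Safety is also judged by other routes: adverse events, laboratory tests and examination (11.1.2, 11.1.3), and bi-weekly review with a stopping rule based on withdrawals (14).

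Most of this stands, and it limits the point to an overstatement and a reporting gap. It does not rescue the sentence. The exploratory label is attached to clinical efficacy, while the assurance about harm carries no qualification. The other safety routes do not estimate an arm difference in FVC or walking distance.

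Four stronger readings are tempting but not supported:

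- **A large worsening would probably be missed.** For 200 mL/year, Step 4 puts a miss above 50% only at the largest assumed SD and only at two-sided 5%. At one-sided 10%, detection is more likely than not at all three SDs.
- **Section 13.3 disclaims power for all three measures.** It names pulmonary function only.
- **The plan will treat a null result as proof of no harm, and a later trial will rely on it.** No section states such a rule or describes a follow-on trial.
- **Section 13.3 excludes estimates.** It promises no interval, but does not rule one out.

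**Conclusion.** The point holds as an overstated property of the design. Section 11.1.1 promises that any harm on these endpoints will be identified; 13.3 contradicts this directly for pulmonary function, and the 20 v 10 arithmetic contradicts it for oxygenation and walking distance. At 0.5 SD the trial would miss the harm in about three of four repetitions (two-sided 5%) or one in two (one-sided 10%). Detection of a harm near 1 SD is likely but not assured.

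The SD-unit results need no outside figure, but rest on full follow-up and the t approximation. The mL figures depend wholly on the assumed SDs. Neither the primary analysis nor the validity of the design is affected. What changes is what the trial may say about harm to lung function, oxygenation and exercise capacity.

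**What to change.** Replace the sentence in 11.1.1 with wording such as:

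> These data will be examined for signals of large detrimental effects. With 20 v 10 subjects the expected 95% CI half-width is about 0.8 SD, and 80% power is reached only for differences of about 1.1 SD (two-sided 5%), so absence of a significant difference will not be taken as evidence of no harm.

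The half-width and the detectable difference should stay separate, as here. What an interval excludes depends on the observed difference, so no fixed excluded range can be stated in advance.

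In 13.3, add the between-arm difference (Hodges-Lehmann or mean) with its 95% CI for FVC, DLCO, SpO2 and 6MWD. Require any statement of no detrimental effect to quote the observed interval limit on the harm side.

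The cost is a few lines of text, one extra table column and a less favourable claim. No additional subjects, visits or measurements are needed.

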- 7.1.4. tolerance of full-dose (2403 mg/day) pirfenidone
- 7.1.5. Positive serology for EBV or CMV

7.2. **Exclusion criteria** will be:

- 7.2.1. FVC $\leq 40\%$ predicted
- 7.2.2. DLCO $\leq 35\%$ predicted (Crapo)
- 7.2.3. FEV1/FVC < 0.7
- 7.2.4. Significant centrilobular emphysema ($> 40\%$ by HRCT)

- 7.2.5. Active tobacco use (cigarette or cigar smoking)
- 7.2.6. Resting SpO₂ on room air <89%
- 7.2.7. listed for lung transplantation defined as being assigned a lung allocation score
- 7.2.8. environmental exposure (occupational, environmental, drug, etc.) felt by the principal investigator (PI) to be the etiology of the interstitial disease
- 7.2.9. diagnosis of collagen-vascular conditions (according to the published American College of Rheumatology criteria)
- 7.2.10. history of unstable or deteriorating cardiac disease
- 7.2.11. acute coronary syndrome, coronary artery bypass, or angioplasty within 3 months of screening
- 7.2.12. uncontrolled arrhythmia
- 7.2.13. uncontrolled hypertension
- 7.2.14. known HIV or hepatitis C
- 7.2.15. known cirrhosis or chronic active hepatitis
- 7.2.16. active substance or alcohol abuse
- 7.2.17. pregnancy or lactation
- 7.2.18. Women of childbearing potential who are not using a medically approved means of contraception. Subjects will be considered of childbearing potential if they are not surgically sterile or have not been postmenopausal for at least 2 years [any subject who is postmenopausal for < 2 years will be required to have a follicle-stimulating hormone (FSH) level to assess her potential to become pregnant
- 7.2.19. clinically relevant lab abnormalities (obtained within 30 days before enrollment), including:
 - 7.2.19.1. creatinine > 2 x upper limit of normal (ULN)
 - 7.2.19.2. hematology outside of specified limits: white blood cells (WBCs) < 3,500/mm³; hematocrit < 25% or > 59%; platelets < 100,000/mm³
 - 7.2.19.3. total bilirubin > 2 x ULN
 - 7.2.19.4. Aspartate (AST) or alanine aminotransferases (ALT) (serum glutamic-oxaloacetic; transaminase [SGOT], or serum glutamic pyruvic transaminase [SGPT]) > 2.0 x ULN
 - 7.2.19.5. alkaline phosphatase > 3 x ULN
 - 7.2.19.6. albumin < 3.0 mg/dL at screening
- 7.2.20. known hypersensitivity to study medication
- 7.2.21. any condition that, in the judgment of the PI, might cause participation in this study to be detrimental to the subject or that the PI deems makes the subject a poor candidate

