- 7.2.22. any therapy with immunosuppressants such as prednisone, azathioprine, or mycophenolate currently or anticipated to be needed during the study period (subjects on these drugs prior to the study will require a 30-day washout period before randomization)
- 7.2.23. participation in another IPF clinical treatment trial during the study period (if completing another IPF clinical treatment trial, then a 30-day washout period is required before randomization)
- 7.2.24. requirement for chronic suppressive therapy with valacyclovir for recurrent herpes virus infection
- 7.2.25. History of myelodysplasia, aplastic anemia, refractory anemia, or multiple myeloma.

8. Study Drug

- 8.1. *Dose justification of valganciclovir:* The standard dosing of valganciclovir for CMV disease when there is active pneumonitis with histopathologic changes such as intracellular inclusions, positive IHC, and acute inflammation is 900 mg twice daily(42). Typically, this occurs in solid organ or bone marrow transplant recipients, and is associated with viremia with viral loads in blood in the range of 10,000-100,000 viral genomes/ml(43). This dose is typically given for 21 days, and can be reduced 900 mg daily to further reduce low-grade viremia (200-2,000 copies/ml), and 900 mg/day can be given long term to prevent relapse or recurrent CMV disease(42). In IPF patients, CMV viral load in BAL is below 10,000 genomes/ml. Hence, the overall viral load is much lower in IPF patients compared to solid organ transplant recipients. Consequently, we believe a dose of 900 mg/day comparable to that used for chronic suppressive therapy in solid organ transplant recipients is most appropriate. A dose of 900

mg/day is generally well tolerated when administered for several months(42), and avoids the bone marrow suppression effects of long-term 900 mg twice daily dosing. Standard dosing of this regimen will be 900 mg once daily.

- 8.2. Justification of treating concomitant EBV and CMV with valganciclovir: Valganciclovir has activity against EBV and CMV. The 50% inhibitory concentration of valganciclovir against EBV is 1.5 mcg/ml(44), and the median area under the concentration versus time curve for 900 mg valganciclovir over 24 hrs (AUC₀₋₂₄) is 29 µg/ml with a peak concentration of 4.4 µg/ml(45). Hence the average concentration of valganciclovir is above the IC50 of EBV. We believe that monotherapy with valganciclovir should be effective and safe for subjects with CMV and EBV.

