- 10.4. Week 12 study visits: This visit will conclude active treatment in the study and will be the primary endpoint for safety and tolerability. In addition, 6 MWT, and oximetry will be performed at this study visit. Subject's diaries will be reviewed, medical history and physical examination will be performed, PFTs will be obtained according to usual clinical care protocol, a pill count will be performed, current medications will be recorded, chemistries/hematology counts will be obtained, and blood will be obtained for biomarker and immunology studies. Subjects who consent to research bronchoscopy will undergo a second research bronchoscopy coordinated with the week 12 study visit.
- 10.5. Week 16 telephone call: 4 weeks after the final study visit (week 12), subjects will be contacted by telephone to review any side effects that occurred while taking study drug.
- 10.6. 6, 9, and 12 month visits: These visits will coincide with routine clinical care visits. Medical history and physical examination will be performed, and PFTs, 6MWT and oximetry will be performed according to usual clinical care protocol studies. A blood sample will be obtained for immunology studies.
- 10.7. Unscheduled disease progression visits: If a subject is found to have new symptoms or worsening of dyspnea or oxygen utilization, the subject will be scheduled for a clinic visit as soon as feasible to reassess secondary endpoints.
- 10.8. Table of Study Visits:

	Screening/ Enrollment Visit	Bronchoscopy Visit (optional)	Week 4 (study visit)	Week 8 (study visit)	Week 12 (study visit)	Week 16 (Teleph one call)	Month 6 (with clinical visit)	Month 9 (with clinical visit)	Month 12 (with clinical visit)
Consent	X								
Randomization	X								
Medical History	X				X				
Physical Exam	X				X				
Blood Chemistry (CMP; CBC, pregnancy test if applicable)	X		X	X	X				
Dispense study drug	X	(X)							
T cell studies from peripheral blood	X	(X)			X		X	X	X
Spirometry Test/DLCO	X				X		X	X	X
6 MWT	X				X		X	X	X

Bronchoscopy (if patient consents)		X			X				
Dispense Study/Review Study Diary for compliance evaluation	X		X	X	X				
Adverse Events			X	X	X	X	X	X	X

11. Data Collection for Specific Aims

11.1. Aim 1: To determine the safety and tolerability of oral valganciclovir as add-on therapy in patients with IPF tolerating standard treatment with pirfenidone.

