11.1.4. Evaluation for change in pulmonary function. PFTs will be captured for all subjects using a CareFusion Sensormedics pulmonary function testing equipment (CareFusion, San Diego, CA), located in the VUMC pulmonary clinic. Measurements will be performed according to current ATS/ERS guidelines(46), and include spirometry (FEV1 and FVC) by NHANES, total lung capacity by body box plethysmography, and diffusing capacity of the lung for carbon monoxide (DLCO) all by %predicted according to Crapo(47). PFTs will be performed by registered respiratory technicians who are experienced in clinical trials. All registered respiratory technicians performing these measurements will be trained in this protocol. All subjects will perform measurements on one machine dedicated to the study to reduce variance.

11.1.5. Change from baseline in daytime resting oxygen requirements. Two measurements will be performed to determine if the research subject has a change in SpO2 or oxygen requirement at rest on each study visit. At each study visit, any supplemental oxygen will be removed for 5 minutes and SpO2 breathing ambient air will then be recorded and evaluated in comparison to baseline. In addition, the patient will have his/her supplemental oxygen requirement determined to maintain oxygen saturation $\geq 88\%$. The change in liters per minute flow rate in oxygen compared to baseline will be recorded.

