- 12.1. Contraindications, precautions, and side effects of study medications: Valganciclovir is FDA approved for the treatment and chronic suppression of herpesviruses, and has a good safety profile post marketing. The dose of valganciclovir recommended for this study is well within the FDA approved dosing range for other indications. The major side effect of valganciclovir is bone marrow suppression causing anemia, leukopenia, or thrombocytopenia. GI upset (nausea and diarrhea) is another reported side effect. These side effects will be monitored by routine laboratory testing and monitoring of subject diaries and direct questioning. Dose adjustments of valganciclovir are required for renal impairment, and dose modifications for renal insufficiency will be made according to recommended guidelines based on estimated creatinine clearance using the Cockcroft-Gault equation. For both valganciclovir and pirfenidone, there are no known major drug interactions requiring special clinical monitoring.
- 12.2. Valganciclovir safety and handling. In animal studies ganciclovir was found to be mutagenic, teratogenic, aspermatogenic and carcinogenic. Valganciclovir is considered a potential teratogen and carcinogen in humans with the potential to cause birth defects and cancers, and may cause temporary or permanent inhibition of spermatogenesis. Women of childbearing age will be required to use a medically approved means of contraception and will have urine pregnancy tests performed with each study visit. Male patients will be advised to practice barrier contraception during and for at least 90 days following treatment with valganciclovir. Tablets will not be broken or crushed. Since valganciclovir is considered a potential teratogen and carcinogen in humans, caution will be observed in handling broken tablets. Direct contact of broken or crushed tablets with skin or mucous membranes will be avoided. If such contact occurs, thorough washing with soap and water, and washing of eyes with sterile water will be performed. Unused medication will be returned to the pharmacy for disposal.

13. Data Management and Statistical Analysis Plan

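### DLCO change is compared between arms with no stated haemoglobin adjustment, so anaemia caused by valganciclovir could be read as lung deterioration at week 12

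*Combined protocol and SAP*

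**What the plan says.** Section 4.2.1 makes change in DLCO a secondary endpoint, to be compared as "diffusing capacity for carbon monoxide (DLCO) in the valganciclovir treated group compared to placebo during active treatment and post-treatment follow-up". Lung function is measured at baseline and at 3, 6, 9 and 12 months.

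Section 11.1.4 describes the measurement. It opens with a general reference, "Measurements will be performed according to current ATS/ERS guidelines(46", and specifies the variable only as "diffusing capacity of the lung for carbon monoxide (DLCO) all by %predicted according to Crapo(47". Section 10.4 adds that the week 12 lung function tests follow the clinic's usual practice. Section 13.3 assigns physiologic endpoints to nonparametric or paired tests, names no covariate, and states that the study is not powered for pulmonary function.

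On the drug, section 12.1 says: "The major side effect of valganciclovir is bone marrow suppression causing anemia, leukopenia, or thrombocytopenia". Section 8.1 expects the once-daily dose to be better in this respect, saying that it "avoids the bone marrow suppression effects of long-term 900 mg twice daily dosing". Neither section gives an anaemia rate.

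On haemoglobin data, the visit table in 10.8 schedules a CBC at screening/enrolment and at weeks 4, 8 and 12. Section 10.4 confirms for week 12 that "chemistries/hematology counts will be obtained". The table schedules no CBC at months 6, 9 or 12, although DLCO is measured then.

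**The concern.** Carbon monoxide uptake depends on haemoglobin in the lung capillaries as well as on the alveolar membrane. This is general measurement knowledge, not something the protocol states. A patient who becomes anaemic shows a lower DLCO even if the lung is unchanged.

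In most comparisons this would be noise shared by both arms. Here the protocol itself says that the active drug can cause anaemia. Such anaemia arises after randomisation and is expected mainly in one arm, so randomisation does not balance it. Week 12 is the end of active treatment, when a drug effect on haemoglobin could still be present.

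Two misreadings are possible. During treatment, a haemoglobin effect could look like lung harm or could mask a lung benefit. After treatment, recovering haemoglobin could look like a DLCO rebound, in a comparison that 4.2.1 explicitly extends into follow-up. Section 11.1.1 gives the clinical measurements a second purpose, the detection of harm from the antiviral drug, so a harm signal of mixed origin matters.

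**Working it through.** **The plan's own figure.** There is none for DLCO: no effect size, SD or power. The only power statement (13.3's companion section 13.2.1) concerns withdrawals and does not enter here.

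**Inputs from the documents.** 20 valganciclovir and 10 placebo subjects (6.1).

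**Assumed inputs.** The two-resistance model of gas transfer; a ratio r of membrane to blood conductance of 0.4 to 1.0 at a reference haemoglobin of 14.6 g/dL; starting haemoglobin 14 g/dL; 20% to 40% of the valganciclovir arm affected (4 to 8 of 20); baseline DLCO 45% predicted; SD of DLCO change 5 to 10 points.

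**Step 1: fall in an affected subject.** 1/DLCO = 1/Dm + 1/(θ·Vc), with θ proportional to haemoglobin h. Scaling θ·Vc to 1 at 14.6 g/dL gives DLCO(h) = 1/(1/r + 14.6/h).

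For r = 0.4: DLCO(14) = 1/(2.5 + 1.0429) = 0.2823 and DLCO(12) = 1/(2.5 + 1.2167) = 0.2691, a relative fall of 4.7%.

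| r | 14 to 12 g/dL | 14 to 10 g/dL |
|---|---|---|
| 0.4 | 4.7% | 10.5% |
| 0.7 | 6.6% | 14.4% |
| 1.0 | 7.8% | 17.0% |

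**Step 2: shift in the arm mean for a 2 g/dL loss.**
- Low: 0.2 × 4.7% = 0.9%
- High: 0.4 × 7.8% = 3.1%

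At 45% predicted this is 45 × 0.009 = 0.4 to 45 × 0.031 = 1.4 points.

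**Step 3: cross-check with a simpler, wider product.** Artefact = baseline DLCO × proportional loss per g/dL × haemoglobin fall × share affected.
- Lowest corner: 36 × 0.02 × 1 × 0.10 = 0.1 points
- Middle: 45 × 0.04 × 2 × 0.25 = 0.9 points
- Highest corner: 60 × 0.07 × 3 × 0.50 = 6.3 points

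The highest corner needs every assumption at its extreme.

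**Step 4: size against the trial's resolution.** By normal approximation at two-sided 5%, the difference detectable with 80% power is SD × √(1/10 + 1/20) × (1.96 + 0.84). This is 5.4 points for SD 5 and 10.9 points for SD 10. A spurious difference of 1 point raises the chance of a significant harm signal from 2.5% to between 4% (SD 10) and 7% (SD 5). A spurious difference of 5 points would raise it to between 25% and 73%. The plan intends nonparametric tests, so these figures are only a guide to scale.

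**The case against.** **The cited standards may already settle it.** Section 11.1.4 refers to guidelines and to a DLCO standardisation paper (reference 47). A reader might infer from the protocol's silence that the laboratory reports uncorrected values. The documents do not support that: they say neither that DLCO is corrected nor that it is not. But reference 46 is titled as a spirometry statement, the content of reference 47 is not reproduced, and nothing identifies a corrected value as the one analysed. The gap in the analysis definition stands.

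**Anaemia may be uncommon or short-lived.** Section 8.1 expects less marrow suppression at this dose, counts are checked at weeks 4, 8 and 12, and section 8.3 holds drug for clinically significant laboratory abnormalities. So it would be too strong to say that drug anaemia will be read as lung deterioration; it could be. These provisions do not remove the problem, because 8.3 sets no haemoglobin threshold and milder falls may not trigger it.

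**The endpoint is exploratory.** Section 4.2 seeks trends, 13.3 disclaims power, and 11.1.1 does not name DLCO among its efficacy measures. This limits the weight of the point. It does not justify leaving in a bias of known direction that is cheap to remove.

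**The data allow interpretation anyway.** A reader might infer that marrow and lung effects could not be separated at all. That goes too far, since week 12 also yields a CBC, FVC and adverse events. But the plan does not say that DLCO will be interpreted in that light.

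**The entry criteria.** Because subjects are excluded only for "hematocrit < 25% or > 59" percent, a reader might infer that the DLCO exclusion in 7.2.2 is also at fault. Baseline haematocrit precedes randomisation and does not bias the arm comparison, so no change to 7.2.2 follows from this point.

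**Conclusion.** The point holds as a conditional one. The plan compares DLCO change between arms, states no haemoglobin adjustment, and names anaemia as an effect of the active drug. If valganciclovir lowers haemoglobin, unadjusted DLCO at week 12 could fall in that arm for a reason outside the lung.

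The plausible size is modest: about 0.9% to 3.1% (relative) in the arm mean, if 20% to 40% of the arm lost 2 g/dL under the two-resistance model. All of these inputs are assumptions. That is well below what 20 versus 10 subjects could detect, so the main risk is a misread trend rather than a false significant result. The safety and withdrawal results are untouched. The change is still worth making, because the bias is caused by treatment, falls on one arm, and can be addressed at week 12 with data already scheduled.

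**What to change.** In sections 4.2.1, 11.1.4 and 13.3:

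- Define the analysed DLCO for the baseline-to-week-12 comparison as haemoglobin-adjusted, and name the adjustment formula in advance.
- Use the CBC nearest each DLCO test. A same-day count cannot be assumed at baseline, because 10.1 accepts clinical tests from the previous 30 days and 10.2 repeats counts only beyond 30 days.
- Report unadjusted DLCO alongside. It still describes total gas transfer, including any effect through anaemia.
- For months 6, 9 and 12, compare unadjusted with unadjusted values, or adjusted with adjusted where a clinical CBC exists. Never mix the two within a comparison.
- State that an apparent rise in DLCO after treatment may reflect haemoglobin recovery.

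The adjustment is applied to each measurement, so it does not conflict with the statement in 13.3 that the study is not powered for multivariate analyses.

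The cost is a few lines of protocol wording and analysis, with no new data for baseline and week 12. The limitation is that follow-up values stay unadjusted wherever no clinical count is available, so the rebound question is flagged but not resolved.
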